#### Biomarker Procedures:

**Salivary Biomarkers Specimen Collection:** At the first data collection visit and last data collection visit, participants will complete saliva collection. Instructions will be given via phone or video. Then the participants will collect the samples themselves. Universal precautions will be used when handling salivary samples. Participants will be instructed to imagine they are chewing a favorite food, slowly moving their jaws in a chewing motion. While doing this, saliva will pool in their mouth. Next, they will gently force the specimen through a short plastic drinking straw into a vial. This passive drool method has been used extensively and has several advantages over a method including volume and less interference with salivary glands. Careful instruction will be given with return demos at the first data collection video/phone visit and reminder instructions at the last data collection visit. Participants will be encouraged to collect specimens the next two days. Each participant will receive a set of pre-labeled, color-coded salivary sample collection tubes, and a similarly color-coded instruction sheet for sample collection times, either via mail, or drop-off at their door using no contact. Samples will be stored in a provided bag in the patient's freezer. Once the participants have completed the samples a study team member will contact them within 48 hours to schedule a pickup of the samples. Specimens will be picked up by the trained study staff using protective equipment including gloves and masks, then transported in a designated cooler to the lab facilities at Johns Hopkins University School of Nursing. Samples for salivary biomarkers will be placed into separate tubes and labeled for freezing at -80°C until batch assayed in duplicate for the respective measurements. Saliva samples will be measured using enzyme immunoassay (EIA) kits from Salimetrics (St. College, PA). A research assistant or the PI will pick up the samples and store in the appropriate freezer at the Johns Hopkins School of Nursing. Samples will be clearly labeled. After all participants have completed each saliva specimen collection (first and last visits) the specimens will be mailed via overnight service to Salimetrics to run in lab.

Commercially available kits will be used for batch assay and each assay will be performed in duplicate. Duplicate assays that demonstrate a coefficient of variation greater than 15% will be reanalyzed. All data

will be de-identified. The sample will be identifiable by a unique generated code. The lab will be blinded and will not have information that could link the generate code to the study participant. Only the PI will have information that will link the unique generated code to the study participant.

Bio specimens for the study will be stored at Salimetrics Laboratory. Salimetrics Laboratory supports protocols by providing facilities, technical experience, and training for non-routine blood and urine biochemical analyses. Salimetrics will also provide necessary kits for the saliva collection. After the saliva analysis is completed and analyzed (~2 years), we will evaluate whether to continue to store the specimens for an additional 3 years or to destroy them. If we decide to destroy the samples at the end of this period, the lab will thaw out the samples and pool them together, then dilute the sample with a bleach solution. This study does not plan to share the bio specimens with other investigators.

Participants will be able to withdraw consent to use their bio specimens, by contacting the PI and putting their request in writing. If a participant decides to withdrawal consent, the PI will contact the lab and the sample will be destroyed as described above.

**Fidelity Plan:** The fidelity plan is based on the NIH Behavior Change consortium developed by national leaders. All of the nurses and data collectors have received training for the Beat the Blues/Get Busy Get Better Dapper Adaptation Protocol. They have all received training on how to measure frailty using the frailty phenotype. We will enhance fidelity through design elements (intervention is distinct and based on theory), training (using an intervention manual and having formal training), delivery (reminder calls the night before intervention sessions, measure fidelity through records of home sessions (by date and duration), checklists completed by study team members, direct observations concerning intervention engagement to evaluate receipt, and enactment (e.g. participants will show the exercises to the nurses). Ten percent of sessions will be audio taped which will be reviewed by the principal investigator using monitoring checklists developed for this pilot trial. The recordings will not be transcribed. When video visits are done the recordings will be recorded via digital recorder and not via the ZOOM recording feature. Feedback will be provided to each interventionist who will provide case presentations in supervisory sessions. Bi-weekly meetings with the data collectors, registered nurses, and the PI.

**Data collection and management:** We will use the Redcap data entry and management system, which is available to all Clinical Translation Science Award (CTSA) sites such as Johns Hopkins University. Data from screening, intervention sessions, and final data collection will be entered onto forms that the data manager will check for completeness and appropriateness. The data manager will send reports of missing or inappropriate entries to the PI every week for clarification and resolution. The details of the Data Safety and Monitoring plan are in the human subjects section.

**Acceptability Qualitative Interviews:** Upon completion of the intervention, the follow up interviews will be scheduled with 10 randomly selected participants from both the intervention and wait list control groups. These interviews will be done by a study team member. The interviews will be scheduled and completed with participants via phone or video. We will ask their thoughts on the intervention and ask for what worked and what did not. The interviews will be audio recorded with a digital recorder only. We will make sure that all information is in a locked file cabinet at Johns Hopkins School of Nursing. We will keep all audio recordings separate from documented person information. We will ask participants to avoid using names in the interviews. The audio recordings will be stored on an encrypted computer after the interviews are completed. The PI will review all transcripts and work with study team to identify themes surrounding intervention changes and conduct intervention mapping to refine the intervention for the next grant application. The audio recordings will be stored on an encrypted computer after the interviews are

completed. Production transcripts will transcribe the follow up interviews. The PI will review all transcripts and work with study team to identify themes surrounding intervention changes and conduct intervention mapping to refine the intervention for the next grant application.

As a additional portion of the study upon completion of the last data collection visit, we would like to call all of the participants who completed the intervention and verify their contact information in order to send them a handout with the study findings. We will verify their address/email and ask if they would like to receive the findings. In addition, we would like to ask participants follow up questions about their participation in the study (please see attached post follow interview guide). Follow up questions will also include acceptability and satisfaction questions in goal attainment. We will also obtain consent for these interview questions using the attached consent script that we will verbally read to them. These interviews will take place via zoom, or telephone and will be recorded with a digital recorder. We will give participants the opportunity to send photos of any goals or changes that were made after completing the study. We will only use recordings for purpose of analyzing goals data and follow up questions. All recordings will be deleted after one year and stored on our encrypted server. Photos will not include any participant identifiers and photos and will not be used for dissemination of findings..

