### **1. Abstract**

Older African American women experience disproportionate rates of chronic conditions in comparison to other groups. Pain, depressive symptoms, and frailty often co-occur in African American women aging with chronic conditions and this combination can lead to disability and poor quality of life. Addressing pain and depressive symptoms may improve or delay the progression to frailty. To our knowledge there is little work being done in this population to address both pain and depression. The Depression and Pain Perseverance through Empowered Recovery (DAPPER) program is person directed and will consist of 8 nurse visits during which the nurse assesses each participant for pain, depression, and frailty, then implements a manualized individually tailored intervention. The data collection visits, and nurse visits will take virtually. We propose a pilot trial that is a wait list randomized control pilot to test the acceptability and obtain a preliminary effect size for the intervention. We will recruit 64 ( $\geq$ age 50) African American women who report pain intensity of 3 or higher that interferes with their activities, depressive symptoms lasting more than two weeks, are pre frail or frail, and live in the community/are not institutionalized. The sample will be recruited through the PI's previous study, community recruitment flyers distributed virtually, and word of mouth campaigns. Participants will be randomized into either the intervention or the wait list control group. Once the intervention group has completed their visits, the wait list control group will begin their visits. All participants will be offered the same information and format of nurse visits. The nurses will systematically tailor the content of the visits to the participants' risk profile and goals based on protocols. All participants will be assessed at the start of the study, at 12 weeks, and 24 weeks. The primary outcomes will be pain, depressive symptoms, and frailty status. Other endpoints include goal attainment, stress (cytokines), self-report, self-efficacy, and communication with health care providers. We will also examine the acceptability of the intervention using intervention compliance and one-on-one qualitative interviews. This study will offer either virtual or in person visits based on the preference of the participants.

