### **2. Objectives**

The aims of this pilot project are to 1) test the Depression and Pain Perseverance through Empowered Recovery (DAPPER) program for feasibility and acceptability. Specifically, we will 1) test the effect size of DAPPER on pain and depressive symptoms from baseline to 12 weeks (compare intervention to wait list control group) and then at 24 weeks to compare the intervention group to wait list control group once again, 2) estimate preliminary effect sizes for DAPPER in reduction of frailty, and 3) measure effect sizes and feasibility of measuring cytokines.

This study is being supported through funding from the Harold Amos Medical Faculty Program and the Johns Hopkins Older Adults Independence Pepper Center.

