After the informed consent process is completed, the IRB approved study team member files the consent document in the research record, including a note confirming the consent process. The data collector will verify if the participant has any questions regarding the consent form and verify the participant understands the consent form. The data collector will ensure that the participant reads the consent form and has a copy of the consent form. After the consent is completed, a formal assessment of outcomes will be done. The data collector will explain the process of saliva sample collection to the participant. We will not collect saliva samples from participants outside of Maryland. A kit will be dropped off to the participants with non-contact either at their door or given to front office. We will call and confirm participants receive the kits. The participants will be asked to store samples in their home refrigerator. If there is not a working refrigerator, the participants will be provided with a cooler and ice packs that will be replaced over the two days. When the participant is ready for the saliva sample to be picked up, they will notify us, and it will be picked up using protective gear (gown, gloves, and mask) without contact with participants and stored in the Johns Hopkins School of Nursing lab.

**Final Data Collection Visit:** At this visit, the data collector will enact the same protocol as at baseline.

**Saliva Sample Visits:** A member of the research staff will contact the participants to ask them a good time to pick up samples. The research staff member will arrive to participants home to pick up samples. Personnel picking up the samples will notify participants when they are arriving, and participants will place the sample outside the front door once the staff member pulls up or walks up to their home location. The staff member will label the specimens and take them directly to the Johns Hopkins School of Nursing refrigerator. Please see specifics below (laboratory studies) for further information about the collection and storage process of the saliva samples.

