**Table 1- Instruments Measuring Main Outcome Variables**

Outcomes	Instruments
Cognition (see inclusion/exclusion criteria)	Short Portable Mini Mental Status Exam 
Depressive Symptoms	Patient Health Questionnaire 9 and Patient Reported Health Outcomes (PROMIS) 57 
Pain	PROMIS Pain Interference, Pain Intensity and Pain Behavior 
Communication	Patients' Reaction Assessment 
Comorbid Conditions	Charlson Comorbidity Index 
ADLS/IADLS	Katz 
Frailty	Frailty phenotype  Frail Scale  will be used to measure frailty.
Stress	Perceived Stress Scale 
Self-Efficacy	Coping and Self-Efficacy Scale 
Readiness to Change	Gitlin and Rose's Readiness to Change Rating System (Gitlin & Rose, )
Social Network Scale	Lubben Social Network Scale
IL6	Saliva Sample
TNF $\alpha$	Saliva Sample
IL8	Saliva Sample
IL-1 $\beta$	Saliva Sample
Goal Attainment	Subjective Report

The following instruments and a demographic questionnaire (e.g. age, SES, and education) will be administered to the participants' pre- and post-intervention.

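### Saliva is scheduled at the first and last data collection visits, not specifically at week 12, so the cytokine effect size may have no untreated comparator

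*Combined protocol and SAP*

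**What the plan says.** The saliva schedule is in Biomarker Procedures: "At the first data collection visit and last data collection visit, participants will complete saliva collection". The shipping instruction repeats it: "After all participants have completed each saliva specimen collection (first and last visits) the specimens will be mailed". The Visits section describes a first and a final data collection visit, and says of the final one: "At this visit, the data collector will enact the same protocol as at baseline". No visible text ties the last visit to a week or an arm.

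The Abstract sets three assessments: "All participants will be assessed at the start of the study, at 12 weeks, and 24 weeks". The design overview under Approach assigns week 12 to comparing intervention with wait list. It assigns week 24 to the wait list's own outcomes and to the intervention arm's course over time.

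The third aim in Objectives is to "measure effect sizes and feasibility of measuring cytokines", with no comparator named. The GEE in Study Statistics (Analytic approach) names depressive symptoms and pain, not cytokines.

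Saliva is taken only from Maryland residents (Visits, Data Collection Visit One).

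**The concern.** Week 12 is the visit the plan itself uses to compare the intervention with a control group that is waiting. The saliva schedule does not name that visit. If the wait list is part-way through or past DAPPER when its second sample is taken, two problems follow:

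- A between-arm cytokine difference at that visit compares treated with treated or partly treated participants.
- A change from baseline within either arm cannot be separated from time trends or regression to the mean.

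Study Statistics says the pilot's effect sizes are for planning a definitive trial. A cytokine estimate near zero, or of the wrong sign, that arose only because the controls had been treated would mislead that planning. Feasibility of collecting and assaying saliva is not at stake.

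**Working it through.** **Step 1: is the wait list treated by its last visit?**

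Text suggesting that it is:
- Abstract: "Once the intervention group has completed their visits, the wait list control group will begin their visits".
- Data Collectors: the final visit is scheduled once the nurse visits are done.
- Text under Table 1: instruments are given "pre- and post-intervention".
- Design overview: week 24 looks at each arm separately.
- Acceptability Qualitative Interviews: interviews after completing the intervention draw on both arms, and the design overview sets them at 24 weeks.

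Text allowing that it is not:
- DAPPER Protocol, wait-list paragraph: the wait list starts only when the intervention group is through the study, which could mean after week 24.
- Objectives, for pain and depressive symptoms: "at 24 weeks to compare the intervention group to wait list control group once again".
- Participants are randomised one by one within 48 hours of baseline, so a start tied to the whole intervention group could leave early enrollees untreated at their own week 24.

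The first reading has more support, but the conflict is not resolved.

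**Step 2: what would a last-visit contrast estimate?**

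The documents give no cytokine effect, so these inputs are assumptions:
- Treatment lowers the cytokine by d SD in either arm.
- The intervention arm keeps a share p of that at its last visit (0.5 to 1).
- In the half-way case, the course lasts 16 weeks with linear build-up. The wait list then starts at week 16 and has had 8 of 16 weeks by week 24. The sample size paragraph mentions 16 weeks only as a follow-up period for attrition.

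The contrast is intervention minus wait list, and the target is -d. Results for d = 0.5:

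| Wait list at its last visit | Formula | p = 1 | p = 0.75 | p = 0.5 |
|---|---|---|---|---|
| Finished DAPPER | (-pd) - (-d) = (1 - p)d | 0.00 | +0.125 | +0.25 |
| Half-way | (-pd) - (-0.5d) = (0.5 - p)d | -0.25 | -0.125 | 0.00 |
| Untreated | -pd | -0.50 | -0.375 | -0.25 |

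If each arm is instead sampled at the end of its own nurse visits, the contrast is -d - (-d) = 0.

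At week 12 with an untreated wait list, the contrast is -d = -0.50 if the nurse visits are complete. On a 16-week course it is -(12/16)d = -0.375.

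All values scale with d. From untreated with p = 1 to finished with p = 0.5, the last-visit range is -0.30 to +0.15 for d = 0.3, and -0.80 to +0.40 for d = 0.8.

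**Step 3: precision.**

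The plan states 25 per arm after attrition. That figure does not reproduce: 64 x 0.87 = 55.68, against a stated 52, and 25 + 25 = 50. This is a separate matter, and the stated 25 is used here. For a baseline-adjusted difference with baseline correlation r, the 95% half-width in SD units is t(0.975, 2n - 3) x sqrt(2(1 - r^2)/n).

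- n = 25, r = 0.5: t with 47 df is 2.012, and 2.012 x sqrt(0.06) = 0.49.
- n = 25, r = 0: 0.57. At r = 0.7: 0.41.
- n = 15 (assumed Maryland subset), r = 0.5: 0.65.

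**The case against.** A reader might infer that the cytokine effect will be attenuated, null or reversed. The documents do not support that as a flat statement, for four reasons.

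- **No between-arm cytokine contrast is stated.** The Objectives name a comparator for pain and depressive symptoms but not for cytokines, and the GEE leaves cytokines out. The wording under Table 1 fits a within-person change. This stands: the cytokine effect size is undefined, and the distortion applies only if it is read as a group difference. The within-person alternative can be estimated, but has no concurrent control.
- **An untreated wait list is possible.** The wait-list paragraph and the second comparison in the Objectives both allow it. The Abstract's crossover sentence also speaks of the group as a whole, so individual randomisation weakens that support too. In the untreated case the contrast survives. With p = 1 and a 16-week course the last visit is even the better time (-d against -0.75d at week 12).
- **Week-12 saliva might be implied or shown elsewhere.** Table 1 lists the cytokines as outcomes, and the design overview measures outcomes at 12 weeks. The wait-list paragraph also has an ambiguous remark about the same data being collected in both arms. The design figure and some text just before the Approach section were not available and could settle the timing. On the visible text, a specific schedule stated twice outweighs a general remark, but does not exclude week 12 beyond doubt.
- **It is a pilot that disclaims power, and this is not a primary outcome.** That limits the importance. Low precision does not remove bias in an estimate meant for planning.

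**Conclusion.** The point holds in limited form. Saliva is not specifically scheduled at the visit used for the arm comparison, the last visit is undefined by arm and week, and the cytokine aim has no comparator. On the better-supported reading, a between-arm contrast at the last visit lacks a fully untreated control and is biased toward zero or beyond: between -0.25 and +0.25 SD when the target is -0.50, under the assumed d, p, course length and build-up. On the other reading it is -0.50 to -0.25 SD, and the contrast survives. The direction of the bias on the first reading follows from the structure. Its size does not come from the documents. With a 95% half-width near 0.5 SD at 25 per arm, and wider in the Maryland subset, the estimate is imprecise at either visit. Feasibility of cytokine measurement is unaffected.

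**What to change.** - Take the second saliva collection at the existing 12-week visit in both arms, before the wait list starts DAPPER.
- Define the cytokine effect size as the baseline-adjusted 12-week group difference with its 95% CI, among participants sampled (Maryland residents).
- Define the last data collection visit by arm and week, and state by which week the eight nurse visits end.
- Reconcile the Abstract, Objectives, design overview, wait-list and Data Collectors paragraphs, the text under Table 1 and the interview section on when the wait list starts.
- If week 12 has already passed for participants, or the last-visit schedule is kept and the wait list has by then started DAPPER, report the cytokine result as uncontrolled within-arm change, not as a between-arm effect.

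**Cost.** No samples are added: at most 64 x 2 = 128 person-collections before and after the change. A protocol amendment is needed. Later post-treatment saliva is lost, including the wait list's only post-treatment sample. If the nurse visits run beyond week 12, the intervention arm is sampled before they end. Labelling a last-visit result as uncontrolled costs nothing.
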